8.3. AEs, SAEs, AESIs and Other Safety Reporting

Timely, accurate, and complete reporting and analysis of safety information, including AEs, SAEs, AESIs (including potential AESIs, refer to Section 8.3.6) and Product Quality Complaints (PQCs), from clinical studies are crucial for the protection of participants, investigators, and the sponsor, and are mandated by regulatory agencies worldwide. The sponsor has established standard

operating procedures in conformity with regulatory requirements worldwide to ensure appropriate reporting of safety information; all clinical studies conducted by the sponsor or its affiliates will be conducted in accordance with those procedures.

AEs will be reported by the participant (or, when appropriate, by a caregiver, surrogate, or the participant's legally acceptable representative) for the duration of the study.

Further details on AEs, SAEs, AESIs, and PQCs can be found in Appendix 2.

8.3.1. Time Period and Frequency for Collecting AE, SAE, and AESI Information

All AEs

AEs and special reporting situations, whether serious or non-serious, that are related to study procedures or that are related to non-investigational sponsor products will be reported from the time a signed and dated ICF is obtained until the end of the study/early withdrawal.

Clinically relevant medical events not meeting the above criteria and occurring between signing of ICF and moment of vaccination will be collected on the Medical History eCRF page as pre-existing conditions.

Solicited AEs, collected through a participant diary, will be recorded from the time of vaccination until 7 days post-vaccination.

All other unsolicited AEs and special reporting situations, whether serious or non-serious, will be reported from the time of vaccination until 28 days post-vaccination.

All SAEs and AEs leading to discontinuation from the study (regardless of the causal relationship) are to be reported from the moment of vaccination until completion of the participant's last study-related procedure, which may include contact for safety follow-up. The sponsor will evaluate any safety information that is spontaneously reported by an investigator beyond the time frame specified in the protocol.

See Section 7.2 for procedures associated with withdrawal of consent.

All AEs will be followed until resolution or until clinically stable.

SAEs

All SAEs occurring during the study must be reported to the appropriate sponsor contact person by study-site personnel immediately, but no later than 24 hours of their knowledge of the event.

Information regarding SAEs will be transmitted to the sponsor using the SAE Form and Safety Report Form of the eCRF, which must be completed and reviewed by a physician from the study site, and transmitted to the sponsor immediately but no later than within 24 hours. The initial and follow-up reports of an SAE should be transmitted electronically or by facsimile (fax). Telephone

reporting should be the exception and the reporter should be asked to complete the appropriate form(s) first.

AESIs

TTS is considered to be an AESI. Thrombotic events and/or thrombocytopenia (defined as platelet count below the lower limit of normal [LLN] range for the testing lab) are considered to be potential AESIs. All AESIs, including potential AESIs, will be reported to the sponsor from the moment of study vaccination until 6 months after the study vaccination (see Section 8.3.6).

8.3.2. Method of Detecting AEs, SAEs and AESIs

Care will be taken not to introduce bias when detecting AEs, SAEs or AESIs. Open-ended and nonleading verbal questioning of the participant is the preferred method to inquire about AE occurrence.

Solicited AEs

Solicited AEs are used to assess the reactogenicity of the study vaccine and are predefined local (injection site) and systemic events for which the participant is specifically questioned and which are noted by participants in their participant diary.

After vaccination, participants will remain under observation at the study site for at least 15 minutes for presence of any acute reactions and solicited events.

In addition, participants will record solicited signs and symptoms in a participant diary for 7 days post-vaccination. All participants will be provided with a participant diary and instructions on how to complete the participant diary (see Overview in Section 8). If a paper diary is used for this study, the study staff will transcribe the information provided by the participant into the relevant sections of the eCRF. If an e-diary is used, diary information will be transferred to the sponsor. After review and verbal discussion of the initial diary entries with the participant, the investigator will complete their own assessment in the relevant sections of the eCRF. Once a solicited sign or symptom from a participant diary is considered to be of severity Grade 1 or above, it will be recorded as a solicited AE.

Solicited Local (Injection Site) AEs

Participants will be asked to note in the participant diary occurrences of injection site pain/tenderness, erythema and swelling at the study vaccine injection site daily for 7 days post-vaccination (day of vaccination and the subsequent 7 days). The extent (largest diameter) of any erythema and swelling should be measured (using the ruler supplied) and recorded daily. The case definitions for solicited injection site events can be found in the references (Gidudu 2012; Kohl 2007).

Solicited Systemic AEs

Participants will be instructed on how to record daily temperature using a thermometer provided for home use. Participants should record the temperature (oral route preferred) in the participant diary in the evening of the day of vaccination, and then daily for the next 7 days approximately at the same time each day. If more than 1 measurement is made on any given day, the highest temperature of that day will be used in the eCRF.

Fever is defined as endogenous elevation of body temperature ≥38.0°C (≥100.4°F), as recorded in at least 1 measurement (Marcy 2004).

Participants will also be instructed on how to note signs and symptoms in the participant diary on a daily basis for 7 days post-vaccination (day of vaccination and the subsequent 7 days), for the following events: fatigue, headache, nausea, and myalgia.

Unsolicited AEs

Unsolicited AEs are all AEs for which the participant is not specifically questioned in the participant diary.

For details regarding AESIs, refer to Section 8.3.6.

Follow-up of AEs, SAEs and AESIs 8.3.3.

The investigator is obligated to perform or arrange for the conduct of supplemental measurements and evaluations as medically indicated to elucidate the nature and causality of the AE, SAE, AESI, or PQC as fully as possible. This may include additional laboratory tests or investigations, histopathological examinations, or consultation with other health care professionals.

AEs and the special reporting situation of pregnancy, will be followed by the investigator as specified in Appendix 2.

8.3.4. **Regulatory Reporting Requirements for SAEs**

The sponsor assumes responsibility for appropriate reporting of AEs to the regulatory authorities. The sponsor will also report to the investigator (and the head of the investigational institute where required) all suspected unexpected serious adverse reactions (SUSARs). The investigator (or sponsor where required) must report SUSARs to the appropriate IEC/IRB that approved the protocol unless otherwise required and documented by the IEC/IRB. A SUSAR will be reported to regulatory authorities unblinded. Participating investigators and IEC/IRB will receive a blinded SUSAR summary, unless otherwise specified.

8.3.5. **Pregnancy**

All initial reports of pregnancy in participants or partners of male participants must be reported to the sponsor by the study-site personnel within 24 hours of their knowledge of the event using the appropriate pregnancy notification form. Abnormal pregnancy outcomes (eg, spontaneous abortion, fetal death, stillbirth, congenital anomalies, ectopic pregnancy) are considered SAEs and must be reported using an SAE reporting form.

If a participant becomes pregnant during the study, a determination regarding study vaccination discontinuation must be made by the investigator in consultation with the sponsor. Follow-up

CONFIDENTIAL – FOIA Exemptions Apply in U.S.

information regarding the outcome of the pregnancy will be required. If the partner of a male participant becomes pregnant during the study, follow-up information regarding the outcome of the pregnancy will be requested upon the consent provided by the partner.

8.3.6. Adverse Events of Special Interest

AESIs (including potential AESIs) are significant AEs that are judged to be of special interest because of clinical importance, known or suspected class effects, or based on nonclinical signals. AESIs and potential AESIs will be carefully monitored during the study by the sponsor.

AESIs and potential AESIs must be reported to the sponsor within 24 hours of awareness irrespective of seriousness (ie, serious and nonserious AEs) or causality following the procedure described above for SAEs.

AESIs must be reported using the AESI form in the eCRF using the eCRF completion guidelines.

Specific requirements for the AESI are described below.

8.3.6.1. Thrombosis with Thrombocytopenia Syndrome

As described in Section 2.2, TTS has been observed very rarely following vaccination with Janssen COVID vaccine and is considered to be an AESI in this study. TTS is a syndrome characterized by a combination of both a thrombotic event and thrombocytopenia. (American Society of Hematology 2021; Brighton Collaboration 2021)

Because this syndrome is rare and not completely understood, all cases of thrombosis and/or thrombocytopenia will be considered a potential case of TTS and should be reported to the sponsor within 24 hours of awareness using the AESI form. Each potential AESI will be reviewed to identify a TTS case. A potential TTS case is defined as:

- Thrombotic events: suspected deep vessel venous or arterial thrombotic events as detailed in Section 10.6, Appendix 6, and/or
- Thrombocytopenia, defined as platelet count below LLN for the testing lab

Symptoms, signs, or conditions suggestive of a thrombotic event or thrombocytopenia should be recorded and reported as a potential AESI even if the final or definitive diagnosis has not yet been determined, and alternative diagnoses have not yet been eliminated or shown to be less likely. Follow-up information and final diagnoses, if applicable, should be submitted to the sponsor as soon as they become available.

In the event of thrombocytopenia, study site personnel should report the absolute value for the platelet count and the reference range for the laboratory test used.

For either a thrombotic event or thrombocytopenia, complete blood count including platelet count and a coagulation profile available from participant's medical records should be entered in the

eCRF. In case these results are not available at the time of the event report in the eCRF, the study site is recommended to obtain a complete blood count including platelet count and a coagulation profile (to be performed at the local laboratory). Repeat testing at the local laboratory may be requested for confirmation upon sponsor discretion.

Aliquots of serum samples collected for immunogenicity tests can be reconverted for participant's safety purposes upon sponsor request (Table 4).

Table 4 provides non-exhaustive list(s) of laboratory tests that may be performed (upon sponsor request).

In addition, the sponsor may request additional laboratory tests on additional blood samples obtained as soon as possible after the potential AESI onset, either during an ad hoc unscheduled visit or the next scheduled visit, whichever comes first. Table 5 provides a non-exhaustive list of laboratory tests that may be requested by the sponsor in case of potential AESI reporting, for which additional samples may be needed.

Table 4: Laboratory Tests That May Be Performed Upon Sponsor Request on Immunogenicity Samples Collected on Day 1, 15, and/or 183 After Potential AESI Reporting

Parameters	Timepoints
 Serum samples for assay such as but not limited to: Heparin Induced Thrombocytopenia (HIT)/PF4 Ab, IgG·(HIT assay) If the above test is positive, also consider: Anti-cardiolipin antibody Beta-2 glycoprotein 	Days 1, 15 and 183 visits (aliquots of serum samples collected for immunogenicity test can be reconverted for participant's safety purposes).

Note: results of the test should be reported in the narrative of the event and/or in the TTS AESI pages of the eCRF.

Table 5: Laboratory Tests That May Be Requested by the Sponsor to be Performed at the Central Laboratory After Potential AESI Reporting

Parameters	Timepoints
Serum/plasma/whole blood samples for coagulation-related assays such as but not limited to: Fibrinogen D-dimer Lupus anticoagulant Anti-cardiolipin antibody Beta-2 glycoprotein Heparin Induced Thrombocytopenia (HIT)/PF4 Ab, IgG·(HIT assay) Platelet activation assay (if HIT/PF4 is positive) Homocysteine COVID-19 serological test	As soon as possible after the potential AESI onset upon sponsor request (during an ad hoc unscheduled visit or the next scheduled visit, whichever comes first).

Note: results of the test should be reported in the narrative of the event and/or in the TTS AESI pages of the eCRF. Irrespective on samples for central laboratory tests collection, relevant data for TTS assessment reported in the medical records of the participant should be reported in eCRF narrative of the event and/or in the TTS AESI pages of the eCRF.

AESIs, including potential AESIs, will require enhanced data collection and evaluation. Every effort should be made to report as much information as possible about the event to the sponsor in a reasonable timeframe. Relevant laboratory results can be entered on the AESI form in the eCRF, using the eCRF completion guidelines.

If the investigator is not the treating physician, every effort should be made to collect the information requested in the form from the treating physician and enter the available information in the eCRF.

If an event meets the criteria for an SAE (Section 10.2.1), it should be reported using the same process as for other SAEs.

Treatment and Follow-up Recommendation

The medical management of thrombotic events with thrombocytopenia is different from the management of isolated thromboembolic diseases. Study site personnel and/or treating physicians should follow available guidelines for treatment of thrombotic thrombocytopenia (eg, American Society of Hematology 2021; British Society of Haematology 2021; CDC 2021). The use of heparin may be harmful and alternative treatments may be needed. Consultation with a hematologist is strongly recommended.

8.4. Medical Resource Utilization

Medical Resource Utilization parameters are not evaluated in this study.

9. STATISTICAL CONSIDERATIONS

Statistical analysis will be done by the sponsor or under the authority of the sponsor. A general description of the statistical methods to be used to analyze the immunogenicity and safety data is outlined below. Specific details will be provided in the Statistical Analysis Plan (SAP).

9.1. Statistical Hypotheses

For a description of the hypotheses, see Section 3.

Non-inferiority of Group 2 versus Group 1 is demonstrated if the 2-sided 95% CI for the GMR (GMT_{Group 2}/GMT_{Group 1}) of the Day 15 pre-F ELISA titers lies entirely above 0.67. If non-inferiority of Group 2 versus Group 1 is not demonstrated, the study fails. If non-inferiority of Group 2 versus Group 1 is demonstrated, then non-inferiority of Group 3 versus Group 1 can be tested: similarly, non-inferiority of Group 3 versus Group 1 is demonstrated if the 2-sided 95% CI for the GMR (GMT_{Group 3}/GMT_{Group 1}) of the Day 15 pre-F ELISA titers lies entirely above 0.67.

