AEs and special reporting situations, whether serious or non-serious, that are related to study procedures or that are related to non-investigational sponsor products will be reported from the time a signed and dated informed consent form (ICF) is obtained until the end of the study/early withdrawal. Solicited AEs, collected through a participant diary will be recorded from the time of vaccination until 7 days post-vaccination. All other unsolicited AEs and special reporting situations, whether serious or non-serious, will be reported from the time of vaccination until 28 days post-vaccination. All SAEs, AESIs, and AEs leading to discontinuation from the study (regardless of the causal relationship) are to be reported from the moment of vaccination until completion of the participant's last study-related procedure, which may include contact for safety follow-up. All AEs will be followed until resolution or until clinically stable.

STATISTICAL METHODS

Sample Size Determination

Sample size calculations are performed under the following assumptions:

- a 10% decrease in GMT of the groups with aged lots (Group 2 and Group 3) versus the group with the non-aged lot (Group 1) (ie, assuming a true GMR of Day 15 pre-F ELISA titers equal to 0.9)
- a standard deviation of 1.3 at the log₂ scale for pre-F ELISA on Day 15^a
- a non-inferiority margin of 0.67 (2/3)
- a 2-sided α of 5%
- hierarchical testing (ie, first Group 2 versus Group 1; if non-inferiority is demonstrated, then Group 3 versus Group 1)

A total of 236 evaluable participants per group are needed to have 95% power to demonstrate non-inferiority for each comparison separately. With this sample size, the overall power to demonstrate non-inferiority of Group 3 versus Group 1 as the second comparison in the hierarchy is at least 90%.

To account for exclusions from the Per-protocol Immunogenicity (PPI) Set (see below for the definitions of analysis sets), dropouts, and missing samples, approximately 250 participants per group should be enrolled.

CONFIDENTIAL – FOIA Exemptions Apply in U.S.

^a Based on the standard deviation of pre-F ELISA at 14 days after vaccine administration observed in Group 14 of study VAC18193RSV1004.

Populations for Analysis Sets

The Full Analysis (FA) Set will include all participants who received study vaccine, regardless of the occurrence of protocol deviations. All safety and participant information analyses will be based on the FA Set.

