9.2. Sample Size Determination

Sample size calculations are performed under the following assumptions:

• a 10% decrease in GMT of the groups with aged lots (Group 2 and Group 3) versus the group with the non-aged lot (Group 1) (ie, assuming a true GMR of Day 15 pre-F ELISA titers equal to 0.9)

- a standard deviation of 1.3 at the log₂ scale for pre-F ELISA on Day 15^a
- a non-inferiority margin of 0.67 (2/3)
- a 2-sided α of 5%
- hierarchical testing (ie, first Group 2 versus Group 1; if non-inferiority is demonstrated, then Group 3 versus Group 1)

A total of 236 evaluable participants per group are needed to have 95% power to demonstrate non-inferiority for each comparison separately. With this sample size, the overall power to demonstrate non-inferiority of Group 3 versus Group 1 as the second comparison in the hierarchy is at least 90%.

To account for exclusions from the Per-protocol Immunogenicity (PPI) Set (see Section 9.3 for the definitions of the analysis sets), dropouts, and missing samples, approximately 250 participants per group should be enrolled.

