10.3. Appendix 3: Regulatory, Ethical, and Study Oversight Considerations

10.3.1. Regulatory and Ethical Considerations

Investigator Responsibilities

The investigator is responsible for ensuring that the study is performed in accordance with the protocol, current ICH guidelines on Good Clinical Practice (GCP), and applicable regulatory and country-specific requirements.

GCP is an international ethical and scientific quality standard for designing, conducting, recording, and reporting studies that involve the participation of human participants. Compliance with this standard provides public assurance that the rights, safety, and well-being of study participants are protected, consistent with the principles that originated in the Declaration of Helsinki, and that the study data are credible.

Protocol Clarification Communications

If text within a final approved protocol requires clarification (eg, current wording is unclear or ambiguous) that does not change any aspect of the current study conduct, a protocol clarification communication (PCC) may be prepared. The PCC Document will be communicated to the Investigational Site, Site Monitors, Local Trial Managers (LTMs), Clinical Trial Managers (CTMs), and/or Contract Research Organizations (CROs) who will ensure that the PCC explanations are followed by the investigators.

The PCC Document may be shared by the sites with Independent Ethics Committees/Institutional Review Boards (IECs/IRBs) per local regulations.

The PCC Documents must NOT be used in place of protocol amendments, but the content of the PCC Document must be included in any future protocol amendments.

Protocol Amendments

Neither the investigator nor the sponsor will modify this protocol without a formal amendment by the sponsor. All protocol amendments must be issued by the sponsor, and signed and dated by the investigator. Protocol amendments must not be implemented without prior IEC/IRB approval, or when the relevant competent authority has raised any grounds for non-acceptance, except when necessary to eliminate immediate hazards to the participants, in which case the amendment must be promptly submitted to the IEC/IRB and relevant competent authority. Documentation of amendment approval by the investigator and IEC/IRB must be provided to the sponsor. When the change(s) involve only logistic or administrative aspects of the study, the IEC/IRB (where required) only needs to be notified.

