2. STATISTICAL HYPOTHESES

To demonstrate the primary objectives, the following hypotheses will be tested sequentially:

Null Hypothesis 1:

Ad26/protein preF RSV vaccine lots representing the critical quality attributes around the intermediate shelf-life (Group 2) induces inferior geometric mean titers (GMTs) of the pre-F ELISA titers on Day 15, compared to Ad26/protein preF RSV vaccine lots representing the critical quality attributes near release (Group 1).

Alternative Hypothesis 1:

Ad26/protein preF RSV vaccine lots representing the critical quality attributes around the intermediate shelf-life (Group 2) induces non-inferior GMTs of the pre-F ELISA titers on Day 15, compared to Ad26/protein preF RSV vaccine lots representing the critical quality attributes near release (Group 1).

Non-inferiority will be shown if the lower limit of the 2-sided 95% confidence interval (CI) around the estimated geometric mean titer ratio (GMR) of the intermediate shelf-life lots versus the release lots (Group 2/Group 1) lies entirely above 0.67.

If non-inferiority is shown for the intermediate shelf-life lots then the following hypotheses will be tested:

Null Hypothesis 2:

Ad26/protein preF RSV vaccine lots representing the critical quality attributes near the presumed end of shelf-life (Group 3) induces inferior GMTs of the pre-F ELISA titers on Day 15, compared to Ad26/protein preF RSV vaccine lots representing the critical quality attributes near release (Group 1).

Alternative Hypothesis 2:

Ad26/protein preF RSV vaccine lots representing the critical quality attributes near the presumed end of shelf-life (Group 3) induces non-inferior GMTs of the pre-F ELISA titers on Day 15, compared to Ad26/protein preF RSV vaccine lots representing the critical quality attributes near release (Group 1).

Non-inferiority will be shown if the lower limit of the 2-sided 95% CI around the estimated GMR (end of shelf-life lots versus release lots [Group 3/Group 1]) lies entirely above 0.67.

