5.3.2. Analysis Methods

The primary immunogenicity objective will be assessed by calculating the 2-sided 95% CIs for the difference in log₂-transformed Day 15 pre-F ELISA titers for each of the comparisons (i.e., Group 2 versus Group 1, and Group 3 versus Group 1).

The CIs will be calculated via an analysis of variance (ANOVA) including all groups (i.e., Groups 1 to 3) with the log₂-transformed Day 15 pre-F ELISA titers as dependent variable and group as independent variable. The CIs around the difference will be back-transformed to CIs around a GMR (GMT_{Group x}/GMT_{Group 1}, where x is 2 or 3) and compared to the non-inferiority margin of 0.67 (2/3).

Non-inferiority of Group 2 versus Group 1 is demonstrated if the 2-sided 95% CI for the GMR (GMT_{Group 2}/GMT_{Group 1}) of the Day 15 pre-F ELISA titers lies entirely above 0.67. If non-inferiority of Group 2 versus Group 1 is not demonstrated, the study fails. If non-inferiority of Group 2 versus Group 1 is demonstrated, then non-inferiority of Group 3 versus Group 1 can be tested: similarly, non-inferiority of Group 3 versus Group 1 is demonstrated if the 2-sided 95% CI for the GMR (GMT_{Group 3}/GMT_{Group 1}) of the Day 15 pre-F ELISA titers lies entirely above 0.67.

As a sensitivity analysis to assess the impact of baseline titers, the primary endpoint will also be evaluated adjusting for the respective baseline titers. In a second sensitivity analysis, different variances between the study groups will be allowed. Therefore, the CIs will be calculated via Welch's ANOVA.

The significance level (α) is 5% (2-sided). As the 2 primary objectives are tested sequentially and as no interim analyses before the primary analysis are planned, no multiplicity adjustments are needed.

The population for analyses related RSV immunogenicity is the PPI set. The choice of population for the different analyses are described in Section 4.

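### Do the pass/fail sentences test against a different margin (0.67) from the one that gives the stated 95% power (2/3)?

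*Protocol*

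**What the plan says.** The margin appears in two forms.

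- **With the fraction.** The sizing assumptions list "a non-inferiority margin of 0.67 (2/3" (Protocol 1.1, repeated in 9.2). The instruction on using the confidence interval also has it: in SAP 5.3.2 the limits are back-transformed "and compared to the non-inferiority margin of 0.67 (2/3" in brackets. Protocol 9.4.3.1 and the Synopsis say the same.
- **Without the fraction.** Every pass/fail sentence has the two-decimal number alone. Protocol 9.1 requires that the interval "of the Day 15 pre-F ELISA titers lies entirely above 0.67". SAP 2 asks that the lower limit for the intermediate shelf-life lots "versus the release lots (Group 2/Group 1) lies entirely above 0.67". Protocol 3 and the Synopsis hypotheses use the same short form.

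On power, Protocol 9.2 says: "A total of 236 evaluable participants per group are needed to have 95% power to demonstrate" non-inferiority in each comparison taken separately. It adds that overall power for the second comparison in the hierarchy is at least 90%. SAP 3 gives no sizing of its own and refers to Protocol 9.2.

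**The concern.** 0.67 and 2/3 are different numbers, and this is the only confirmatory threshold in the trial. It decides Group 2 versus Group 1, and through the hierarchy it controls whether Group 3 versus Group 1 is tested at all. A lower limit between 0.6667 and 0.6700 would pass under one reading and fail under the other. Nothing in either document says outright that the comparison uses the unrounded fraction. Protocol 3, Protocol 9.1 and SAP 2 never show the fraction, so someone working from those sections alone would see a plain two-decimal cut-off.

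If a limit fell in that gap, the choice of reading would be made with the result known, and choosing 2/3 could look like relaxing the written rule. The stated sample size also fits only one of the two numbers, which suggests that the power statement and the decision rule rest on different thresholds.

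**Working it through.** **Inputs (Protocol 9.2):** SD 1.3 on the log2 scale, true GMR 0.9, two-sided 5% (one-sided 2.5% at the lower limit), 236 evaluable per group, target power 95%.

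**Distance from the true ratio to the margin**, log2(0.9) − log2(margin):

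- 2/3: −0.1520 + 0.5850 = 0.4330
- 0.67: −0.1520 + 0.5778 = 0.4258

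The gap between the two is 0.0072 on the log2 scale.

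**Sample size, normal approximation**, n = 2 × [SD × (1.960 + 1.645) / distance]²:

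- 2/3: 2 × (1.3 × 3.605 / 0.4330)² = 234.3, so 235
- 0.67: 2 × (1.3 × 3.605 / 0.4258)² = 242.3, so 243

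With the noncentral t, the smallest n for 95% power is:

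| Degrees of freedom | 2/3 | 0.67 |
|---|---|---|
| Two-group (2n − 2) | 236 | 244 |
| Three-group ANOVA (3n − 3) | 235 | 243 |

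The plan's 236 is therefore reproduced exactly by a standard calculation with 2/3, and by none of the three methods with 0.67. The sizing used 2/3.

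**Power per comparison.** The standard error is 1.3 × √(2/236) = 0.1197. With three-group degrees of freedom:

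| Evaluable per group | 2/3 | 0.67 |
|---|---|---|
| 236 | 95.1% | 94.4% |
| 250 | 96.1% | 95.5% |

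**Overall power for both comparisons at 236.** Simulating the three-group ANOVA with a shared control and pooled SD (3 million runs) gives 91.4% with 2/3 and 90.3% with 0.67. The claim of at least 90% holds either way. Treating the comparisons as independent would give 0.9444² = 89.2% for 0.67. The shared control makes the two results positively correlated, and that brings the figure above 90%.

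**Observed GMR needed to pass at 236**, margin × 2^(1.963 × 0.1197):

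- 2/3: 0.785
- 0.67: 0.789

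**How often the reading matters at a true GMR of 0.9.** The lower limit falls between 2/3 and 0.67 with probability 0.9508 − 0.9444 = 0.0064, or 0.6% per comparison. At least one of the two sequential conclusions changes in about 1.2% of trials.

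**Error rates across readings.** The 0.67 rule passes 2.2% of the time when the true GMR is exactly 2/3, which is below 2.5%. The 2/3 rule passes 2.9% of the time when the true GMR is exactly 0.67.

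**The text.** In SAP 5.3.2 and Protocol 9.4.3.1 the paragraph that compares the interval with 0.67, glossed as 2/3, comes directly before the paragraph stating when non-inferiority is shown. The first defines the number and the second uses it in short form.

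**The case for a change.** The best case for acting is that the ambiguity concerns the single confirmatory threshold, costs one SAP sentence to remove, and can be settled credibly only before unblinding. The bracket is absent from every pass/fail sentence. It could also be read as noting where a literal 0.67 came from, rather than as defining 0.67 to be 2/3. If literal 0.67 were the intended margin, applying 2/3 would carry 2.9% one-sided error instead of 2.5%, and the stated 95% power at 236 would be slightly too high. The route for a fix exists: Protocol 9 leaves details to the SAP ("Specific details will be provided in the Statistical Analysis Plan (SAP"), and Protocol 10.3.1 provides clarification communications for unclear text ("If text within a final approved protocol requires clarification (eg, current wording is unclear or ambiguous").

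Some of this stands. The short form does appear without the fraction in Protocol 3, Protocol 9.1 and SAP 2, the arithmetic is right, and adding the fraction there would do no harm. The claim of a conflict does not stand. The sizing and the CI-comparison instruction both equate 0.67 with 2/3, no section proposes another value, and 236 confirms which number the authors used. That the comparison is not explicitly called unrounded is no defect either. Neither document says that limits are rounded before comparison, and full precision is the normal default for an interval formed on the log2 scale and back-transformed.

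**Conclusion.** The concern does not hold as an arithmetic error, and no change follows. The plan has one margin, 2/3, written as 0.67 for short, and 236 per group with 95% power is correct for it. What is left is a drafting shorthand that an analyst following SAP 5.3.2 would resolve as intended.

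If someone did apply literal 0.67, the trial would still be sound. The rule would be stricter, so it could not inflate type I error against 2/3. Per-comparison power at 236 would fall by about 0.6 percentage points, and overall power would stay above 90%. Enrolment of 250 per group would still give 95% power with up to 2.8% loss, (250 − 243)/250, against 5.6% with 2/3, (250 − 236)/250. The readings would differ in roughly 1 trial in 160 per comparison (1/0.0064).

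These figures rest on the plan's assumptions of SD 1.3 on log2 and a true GMR of 0.9 for both aged-lot groups, and on equal group sizes.
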